##### 3.1.2 Overall Design and Control Methods

###### Trial Design

This is a multi-center, randomized, assessor-blind, controlled trial to compare the occurrence of MACEs in patients with prostate cancer and concurrent CVD receiving either monthly treatment with degarelix or leuprolide 3-month depot for 1 year. Patients will be screened within 21 days prior to randomization for compliance with the inclusion and exclusion criteria. A trial design diagram is provided in [Figure 1](#).

Patients will be randomized to one of the two treatments in a 1:1 ratio stratified by baseline age group and region, as detailed in Section 4.2.2. After randomization, the management of prostate cancer is intended to reflect standard-of-care. Monitoring for possible MACEs will occur throughout the trial applying a specific Clinical Events Classification (CEC) process ensuring blinding of the assessors as described in Section 7.1.1.

Patients should be evaluated by a CV specialist to ensure that their CVD treatment is according to standard-of-care before trial entry. Cardiovascular disease information and source medical documents will be requested by the Investigator from the patient's CV specialist to evaluate and document CVD history for eligibility, using a Medical / CV History Request Form. A process will be implemented for the collection and review of supporting source data (with the involvement of the contract research organization [CRO] and Duke Clinical Research Institute [DCRI]) to ensure

the accuracy of patients' medical records documentation for the CVD-related inclusion criteria. The Investigator should ensure that pre-existing CVD and any CVD that may be diagnosed during the trial is managed by a CV specialist according to standard clinical practice. After randomization, the management of CVD and prostate cancer is intended to reflect standard-of-care.

If a patient experiences a CV event during the course of the trial, the Investigator will be encouraged to let the patient continue in the trial if this is not considered to constitute a safety concern. Patients who prematurely withdraw from the trial or from treatment with investigational medicinal product (IMP) will be followed-up for potential CV events and hospitalizations throughout the trial period as described in Section 4.4. If a patient is lost to follow-up, all attempts have to be made to obtain the vital and medical status of the patient at the planned end-of-trial for the patient.

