#### **4.4 Withdrawal Criteria**

The patients have the right to withdraw from IMP treatment and/or the trial at any time for any reason without the need to justify their decision.

Withdrawal of consent for treatment should be distinguished from withdrawal of consent for follow-up visits/telephone contacts and from withdrawal of consent for non-patient contact follow-up, e.g., medical records checks. Therefore, when giving written consent for participation in the trial, patients will also be specifically asked to give written consent to safety follow-up procedures that will take place in case of withdrawal from IMP treatment, and/or in case a patient is lost to follow-up.

Patients should be informed that not giving consent, or requesting withdrawal of consent for safety follow-up, will jeopardize the public health value of the trial. Withdrawal of consent for safety follow-up should be accompanied by documentation of the reason for withdrawal.

Patients who withdraw from IMP treatment and/or the trial should be explicitly asked about the contribution of possible adverse events to their decision to withdraw consent, and any adverse event information elicited should be documented.

Preferably the patient should withdraw consent in writing and, if the patient or the patient's representative refuses or is physically unavailable, the trial site personnel should document and sign the reason for the patient's failure to withdraw consent in writing.

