The Investigator also has the right to withdraw patients from the trial or from treatment with IMP. Since an excessive rate of trial withdrawals or IMP treatment withdrawals can render the trial devoid of meaning, the unnecessary withdrawal of patients should be strictly avoided and all necessary measures should be taken to prevent withdrawals/discontinuations from IMP treatment. In case of the occurrence of any CV event, the Investigator will be encouraged to let the patient continue in the trial as per protocol if this is not considered to constitute a safety concern.

---

a **Note:** *In the UK, the following paragraph is applicable instead:*

In case a patient is lost to follow-up, despite every attempt (e.g., certified mail, telephone contact of patient or patient relatives) to get in contact, the vital and medical status of the patient should be investigated an additional last time at the end of the trial for that patient (i.e. 12 months after Visit 1), by accessing the patient's hospital records, or publicly available sources such as national registries and newspaper obituaries. Attempts may also be made to contact the patient or his relatives to ascertain this information. However, the patients have the right to withdraw their consent for collection of this information at any time, without the need to justify their decision.

Reasons for discontinuation from the trial or treatment with IMP include:

- Significant non-compliance to trial protocol, as judged by the Investigator and/or the Sponsor
- Other medical or safety reasons, as judged by the Investigator and/or the Sponsor

Patients discontinued from the trial will not be replaced.

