## **9.6 Endpoint Assessments**

### **9.6.1 General Considerations**

The analysis of efficacy will be performed for the FAS. Unless otherwise specified, time to event endpoints will be censored at the time of treatment discontinuation, initiation of prohibited therapies related to hormonal therapy, lost to follow-up/withdrawal from the trial or Day 336, whichever occurs first. In addition, all hypothesis tests will be two-sided at a significance level of 5% and missing data will not be imputed. 95% confidence limits and the associated p-values will be presented for estimates of the treatment effect comparing degarelix to leuprolide for all regression analyses. P-values will be presented for all non-parametric tests, such as the log-rank test.

All regression models analyzing the time to MACE or the time to components of the MACE composite endpoint will be adjusted for the following CV risk factors measured at baseline: waist circumference, body mass index (BMI), [REDACTED] blood pressure, diabetes status, cholesterol and triglyceride levels. All semi-parametric and non-parametric models will be stratified by baseline age group and region.

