9.2.2 Sensitivity Analyses

9.2.2.1 Sensitivity Analysis: Time from randomization to the first confirmed (adjudicated) occurrence of non-fatal myocardial infarction, non-fatal stroke, non-fatal unstable angina requiring hospitalization, or all-cause death

Time from randomization to the first confirmed (adjudicated) occurrence of non-fatal myocardial infarction, non-fatal stroke, non-fatal unstable angina requiring hospitalization, or all-cause death is defined similarly as the primary endpoint with the addition of cardiovascular events unstable angina requiring hospitalization. Also, the endpoint will be analyzed as for the primary endpoint.

9.2.2.2 Sensitivity Analysis: Time to first confirmed occurrence of a MACE related adverse event (MI SMQ (broad); Central nervous system hemorrhages and cerebrovascular conditions SMQ (broad); all-cause death)

Time to first confirmed occurrence of a MACE related adverse event is defined as for the primary endpoint with events being; any adverse event within the broad SMQ term 'myocardial infarction', any adverse event within broad SMQ term 'Central nervous system hemorrhages and cerebrovascular conditions' or all-cause death. Also, the endpoint will be analyzed as for the primary endpoint.

9.2.2.3 Sensitivity Analysis: Total occurrence of (adjudicated) myocardial infarction, stroke, and all-cause death

Total occurrence of myocardial infarction (MI), stroke and all-cause death is defined as the total number of events (MI, stroke or death) occurring over the duration of the trial.

The endpoint will be compared between treatment groups using a negative binomial model. The estimated treatment difference with a 95% confidence interval will be presented.

9.2.2.4 Sensitivity Analysis pertaining to treatment discontinuation or initiation of prohibited therapies related to hormonal therapy

For the purposes of this sensitivity analysis, patients will NOT be censored at the time of treatment discontinuation or initiation of prohibited therapies related to hormonal therapy. Rather, information pertaining to all observed occurrences of the first adjudicated MACE event in patients randomized in the study will be used. Patients will be censored at lost to follow-up/withdrawal from study or day 336, whichever occurs first.

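### A staff decision to withdraw a patient from the trial ends MACE counting even in SAP 9.2.2.4, the one time-to-event analysis meant to look past treatment stops

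*Protocol*

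**What the plan says.** **Who may withdraw, and from what.** Protocol 4.4 states: "The Investigator also has the right to withdraw patients from the trial or from treatment with IMP". The list that follows is introduced by "Reasons for discontinuation from the trial or treatment with IMP include", so its two reasons serve both levels. They are "Significant non-compliance to trial protocol, as judged by the Investigator and/or the Sponsor" and other medical or safety reasons, judged by the same parties. The section gives no criteria and no blinded or independent approval. Its restraint is the statement that "the unnecessary withdrawal of patients should be strictly avoided", plus encouragement to keep patients in after a CV event.

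**Follow-up afterwards.** Protocol 3.1.2 says that patients who leave the trial or IMP early "will be followed-up for potential CV events and hospitalizations throughout the trial period", and refers to 4.4 for the procedure. Protocol 8.2.3 says the same for premature trial discontinuation. Section 4.4 itself describes monthly telephone contact after IMP discontinuation or prohibited medication, and a final status check for patients lost to follow-up. It bars new eCRF data only when the patient withdraws consent including follow-up.

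**Censoring.** The general rule in Protocol 9.6.1 and SAP 9.1 censors at treatment discontinuation, prohibited hormonal therapy, or "lost to follow-up/withdrawal from the trial or Day 336, whichever occurs first". The sensitivity analysis in Protocol 9.6.2 and SAP 9.2.2.4 removes the first two censoring points and keeps the rest: "Patients will be censored at lost to follow-up/withdrawal from study or day 336, whichever occurs first".

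**The concern.** Non-compliance and medical reasons can be grounds for ending injections. They do not make a later infarction, stroke or death uninformative about the randomized comparison. Section 4.4 does not separate the two levels, so a judgement about conduct or health, made by people who can know the arm, can also end endpoint counting.

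This bears on SAP 9.2.2.4 in particular. The primary analysis is on-treatment by construction: it stops counting when IMP stops. A reader who worries that stopping IMP is related to prognosis, or differs by arm, will turn to 9.2.2.4 for reassurance. If some of the same patients also drop out of that analysis through a discretionary route, the check has part of the weakness that it is meant to test.

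**Working it through.** **Step 1: trace one patient.** Take a patient whom the Investigator withdraws from the trial at Day 100 for non-compliance, who withdraws no consent and has an infarction at Day 200.

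| Question | Source | Answer |
|---|---|---|
| May the Investigator do this? | Protocol 4.4 | Yes |
| Should the infarction be collected? | Protocol 3.1.2, 8.2.3 | Yes, by the procedure in 4.4 |
| Does 4.4 give that procedure for trial-level withdrawal? | Protocol 4.4 | Not in terms; monthly calls are tied to IMP discontinuation or prohibited medication |
| Is entry in the eCRF barred? | Protocol 4.4 | No; only the patient's withdrawal of consent, follow-up included, bars it |
| Counted in the primary analysis? | Protocol 9.6.1, SAP 9.1 | No; already censored at IMP discontinuation |
| Counted in the follow-all analysis? | Protocol 9.6.2, SAP 9.2.2.4 | No; censored at trial withdrawal |

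Had the same patient been withdrawn from IMP only, the last answer would be yes. The label chosen at Day 100 decides it.

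**Step 2: look for another analysis that counts him.** SAP 9.2.2.1 and 9.2.2.2 are analysed as the primary endpoint, so they also censor at IMP stop. SAP 9.2.2.3 is a negative binomial count of total events over the trial with no stated censoring rule; it might include him, but it is not a time-to-event analysis. So 9.2.2.4 is the only time-to-event analysis that relaxes the on-treatment rule.

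**Step 3: size, as illustration.** The documents give no rate of staff-initiated withdrawal. SAP 3.2.3 gives Z ≈ log(1/HR) × √(d/4). As a check on the formula, Z = 0.7 at d = 33 gives HR = exp(−0.7/√8.25) = 0.784 (Table 1: 0.78). Z = 1.96 at d = 66 gives exp(−1.96/√16.5) = 0.617 (Table 1: 0.61).

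Now assume that the true HR is 1 and that a fraction f of degarelix events, but no leuprolide events, goes uncounted. The apparent HR is about 1 − f. With d held fixed, the chance of a nominally significant result favouring degarelix is 1 − Φ(1.96 + ln(1 − f) × √(d/4)), against 2.5% when f = 0.

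| f (assumed) | d = 66, √(d/4) = 4.062 | d = 14, √(d/4) = 1.871 |
|---|---|---|
| 5% | 1 − Φ(1.752) = 4.0% | 1 − Φ(1.864) = 3.1% |
| 10% | 1 − Φ(1.532) = 6.3% | 1 − Φ(1.763) = 3.9% |
| 20% | 1 − Φ(1.054) = 14.6% | 1 − Φ(1.543) = 6.1% |

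The second column uses the 14 patients with positively adjudicated events reported in SAP section 3. The SAP does not say how many of those came after an IMP stop or a trial withdrawal. At 14 events the 95% interval for the HR spans a factor of exp(1.96/√3.5) = 2.85 either way, so chance outweighs a bias of this size. Loss in the leuprolide arm would bias in the other direction. Loss at the same rate in both arms and unrelated to outcome would cost only some precision.

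**The case against.** The strongest reply is that the wording of 9.2.2.4 already covers the case. Just before its censoring rule, it says that all observed first adjudicated MACEs in randomized patients will be used. With 3.1.2 and 8.2.3 requiring follow-up, and 4.4 stopping data entry only on the patient's withdrawal of consent, withdrawal from study could be taken to mean the end of observation. That reading is sensible, and it is what the fix below writes down. It does not settle the matter as the text stands. The explicit censoring sentence follows and limits the general one, the term is undefined, and 4.4 uses withdrawal from the trial for a decision that the Investigator may take.

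The plan also has safeguards. Section 4.4 discourages withdrawal. Protocol 11.2 has monitors check the follow-up of patients who stopped treatment, and 11.3 has site patterns of suspected MACE reporting reviewed centrally. SAP section 4 plans discontinuation curves by reason and arm, with a log-rank comparison of discontinuation rates between arms. These could reveal an imbalance, so it would be wrong to call the problem undetectable. They would not restore an uncounted event.

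Four stronger readings are tempting, and the documents do not support them:

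- *The primary result is exposed.* Stopping IMP already censors in the primary analysis, and SAP 9.2.1 ties trial success to that analysis. With so few events one might infer that a single withdrawn patient could decide the outcome, but this route does not alter the primary test.
- *Every MACE analysis censors at trial withdrawal.* SAP 9.2.2.3 states no censoring rule.
- *An unblinded Sponsor can remove patients.* The stated right is the Investigator's; the Sponsor appears as a possible judge of the reasons. That the Sponsor knows the arm is an inference from open-label products and its monitor's drug accountability checks (Protocol 5.6.1). The Sponsor is stated to be blinded to adjudicated MACE data.
- *Consent to follow-up should be a condition of entry.* Section 4.4 warns that "not giving consent, or requesting withdrawal of consent for safety follow-up, will jeopardize the public health value of the trial", from which one might infer that a patient can enrol without giving that consent. Making it an eligibility rule is a separate trade-off against enrolment, and this point does not need it.

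**Conclusion.** The point holds for SAP 9.2.2.4 and its counterpart in Protocol 9.6.2, and for the gap between Protocol 3.1.2 and 8.2.3 on one side and 4.4 on the other. As written, events after a staff-initiated trial withdrawal are to be collected, but the procedure for collecting them is not set out, and the follow-all analysis leaves them out. Protocol 9.3 says that no protocol deviation will exclude data from the efficacy analyses; censoring after removal for non-compliance sits badly with that.

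The issue is possible bias in a supporting analysis. It does not affect alpha, the 66 events, the 876 patients or the primary test. Its actual size is unknown: the 4.0% to 14.6% at 66 events, and 3.1% to 6.1% at 14, rest on an assumed one-sided loss of 5% to 20% of degarelix events under equal hazards. If no patient was withdrawn from the trial by staff decision, the effect is nil. The repair is still worth making, because it costs almost nothing and 9.2.2.4 is the only time-to-event analysis available to test the on-treatment censoring.

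**What to change.** 1. **SAP 9.2.2.4 and Protocol 9.6.2 (sensitivity analysis).** Define withdrawal from the trial or study, for censoring, as the patient's withdrawal of consent to follow-up. Keep true loss to follow-up and Day 336 as the other censoring points. Adjudicated MACEs after a staff-initiated withdrawal then count.
2. **SAP section 4.** Report the number of staff-initiated trial withdrawals by arm and reason, kept apart from the patients' own withdrawals, with the number who had an adjudicated MACE afterwards.
3. **Protocol 4.4.** State that a decision by the Investigator or Sponsor ends IMP only. State also that endpoint follow-up to Day 336 continues through the existing monthly contacts unless the patient dies, withdraws consent to follow-up or is lost to follow-up. This supplies the procedure to which 3.1.2 and 8.2.3 refer, and leaves the grounds for stopping treatment as they are.

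Cost: one definition, one table and a few lines of protocol text; no change to alpha, events or sample size. SAP section 3 records early termination with 545 patients randomized, so items 1 and 2 are what can still be acted on. They can recover only events that sites collected and sent for adjudication. Item 3 is a correction to the design.

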## 5 TREATMENTS

### 5.1 Treatments Administered

A treatment flow chart is provided in [Table 2](#).

Patients randomized to **degarelix** will receive:

#### Start of treatment (Month 0):

- A starting dose of 240 mg degarelix at a concentration of 40 mg/mL, administered as subcutaneous (s.c.) injections in the abdominal region via two equivalent injections of 120 mg each. The volume of each injection is 3.0 mL.

#### Month 1-11:

- Eleven (11) maintenance doses of 80 mg degarelix at a concentration of 20 mg/mL, administered at monthly (28-day) intervals as s.c. injections in the abdominal region via one injection of 80 mg, i.e. the volume of each injection is 4.0 mL.

Detailed administration guidelines for degarelix are given in the current national FIRMAGON label.

Patients randomized to **leuprolide** will receive:

#### Start of treatment (Month 0):

- One dose of 22.5 mg leuprolide, administered as a single i.m. injection according to the directions for use in the manufacturer's current national label. The volume of the injection is 1.5 mL.

#### Month 1-11:

- Three (3) doses of 22.5 mg leuprolide, administered as i.m. injections every 3 months (Month 3, 6, and 9) according to the directions for use in the manufacturer's current national label. The volume of each injection is 1.5 mL.

### 5.2 Characteristics and Source of Supply

All IMPs are provided by the Sponsor and will be handled according to the principles of Good Manufacturing Practice (GMP).

#### Degarelix

Degarelix is provided as commercially available kits for Starting Dose and Maintenance Dose:

- Starting Dose kit contains 2 sets of: 120 mg vial with powder for injection, prefilled syringe with 3 mL Sterile Water for Injection, vial adapter and administration needle (2 x 3.0 mL is withdrawn to deliver 240 mg degarelix at a concentration of 40 mg/mL)

- Maintenance Dose kit contains 1 vial with 80 mg powder for injection, prefilled syringe with 4.2 mL Sterile Water for Injection, vial adapter and administration needle (4.0 mL is withdrawn to deliver 80 mg degarelix at a concentration of 20 mg/mL)

## **Leuprolide**

Leuprolide acetate is provided as commercially available kits containing one prefilled dual chamber syringe containing sterile lyophilized microspheres which, when mixed with diluent, become a suspension intended as an i.m. injection for 3-month administration (LUPRON DEPOT 22.5 mg).

### **5.3 Packaging and Labelling**

Packaging and labelling of the IMPs will be performed under the responsibility of the Sponsor's IMP Department in accordance with GMP and national regulatory requirements.

Country-specific labels of the IMPs will be used. The labels will contain a self-adhesive tear-off portion to be affixed to the drug dispensing log maintained at the trial site. All products will be uniquely numbered with IMP number.

### **5.4 Conditions for Storage and Use**

The Investigator will ensure that the IMP will be stored in appropriate conditions in a secure location with controlled access. The temperature in the storage compartment will be monitored regularly and the values shall be documented. Deviations in storage temperature must be reported without delay, and the IMP must not be used until further instructions from the Sponsor are received.

The products must be stored and handled in accordance with the commercial product label information.

### **5.5 Blinding / Unblinding**

This is an assessor-blind trial. As described in Section 3.5.3, adjudication and classification of CV events for primary endpoint analysis will be performed by an external independent CEC Committee (Section 3.4.1) throughout the trial. Adjudicated MACE data for the pre-planned and unblinded interim analysis of the primary endpoint (Section 9.9) will be transferred directly from the CEC Committee to the DSMB (Section 3.4.2) in order to keep those data blinded to the Sponsor.

### **5.6 Treatment Compliance**

#### **5.6.1 Dispensing and Accountability**

The IMPs will only be dispensed to patients who meet the eligibility criteria and are randomized to a treatment group in the trial. The IMP will be administered to the patient by authorized dedicated trial drug administrators at the trial sites.

The allocation of the IMP kits will be done through an Interactive Response Technology system. The administration of IMP should be documented at the site in the subject dispensing log. This is to include IMP kit number, batch numbers, expiration date and date and time of administration.

The dedicated monitor (a Sponsor representative) will verify the drug accountability during the trial. IMP carton kits (secondary packaging only) will be saved for drug accountability.

